## 3.4.3. E-Diary Completion

An e-diary will be considered transmitted if any data for the local reactions and systemic events are present for any day. If all data are missing for all items (local reactions and systemic events) on the e-diary for all 7 days after vaccination, then the e-diary will be considered not transmitted. An e-diary will be considered transmitted for a given day if any data are present for that day.

## 3.4.4. Nonstudy Vaccines

Any nonstudy vaccinations received from 28 days prior to study enrollment through the conclusion of study participation will be collected.

Nonstudy vaccinations will be categorized according to the latest version (at the time of reporting) of the WHODrug Dictionary.

#### 3.5. Safety Endpoints

#### 3.5.1. Vital Sign Data

The temperature collected at baseline will only be used to assess any potential protocol deviation for vaccination temporary delay. Therefore, it will not be included as a baseline variable.

#### 3.5.2. Adverse Events

Tier 1 events: As this is a Phase 1 study, only Tier 1 AEs requested by FDA will be analyzed (Section 6.6.1). These are prespecified events of clinical importance and are maintained in a list in the product's safety review plan.

Guillain-Barre syndrome, acute polyneuropathy, atrial fibrillation (occurring from vaccination through the 1-month follow-up visit), preterm delivery (occurring from vaccination through the end of the study), preterm birth (occurring from vaccination through the end of the study) will be included as the Tier 1 event analysis for RSVpreF. The derivation for Guillain-Barre syndrome and acute polyneuropathy is from Day 1 through Day 43 after vaccination (Day 1 is the vaccination day). The RSV program Tier 1 list of MedDRA PTs is maintained by the safety risk lead in the CAETeLiSt and is referenced in the safety surveillance review plan for the program. The current list of Tier 1 events referenced by this study for RSVpreF should be confirmed to ensure that appropriate Tier 1 events will be used to produce final tables/graphs before conducting an analysis.

Note that the denominator for calculating the preterm delivery, preterm birth, and hypertensive disorders of pregnancy would be the number of pregnant women.

As this is a Phase 1 study, no additional tiered AEs are planned for any analysis.

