1.3. Schedule of Activities

The SoA table provides an overview of the protocol visits and procedures. Refer to the Study Assessments And Procedures section of the protocol for detailed information on each procedure and assessment required for compliance with the protocol.

The investigator may schedule visits (unplanned visits) in addition to those listed in the SoA table, in order to conduct evaluations or assessments required to protect the well-being of the participant.

1.3.1.

Visit Number Abbreviations used in this table may be found in Appendix 7.	1	2	3	4	Notes
Visit Description	Screening and Vaccination	1-Week Follow-Up Visit		6-Month Follow-Up Visit	
Visit Window (Days)	Day 1	6 to 8 Days After Vaccination Day 1	28 to 35 Days After Visit	175 to 189 Days After Visit 1	Day relative to start of study intervention administration (Day 1).
Type of Visit	Clinic	Telehealth	Clinic	Telehealth	
Obtain informed consent and assent (if applicable)	X				Informed consent should be obtained prior to undergoing any study-specific procedures. See Section 10.1.3 for additional information.
Assign participant number	X				
Obtain demography and significant medical history data	X				

Visit Number Abbreviations used in this table may be found in Appendix 7.	1	2	3	4	Notes
Visit Description	Screening and Vaccination	1-Week Follow-Up Visit	1-Month Follow-Up Visit	6-Month Follow-Up Visit	
Visit Window (Days)	Day 1	6 to 8 Days After Vaccination Day 1	28 to 35 Days After Visit	175 to 189 Days After Visit 1	Day relative to start of study intervention administration (Day 1).
Type of Visit	Clinic	Telehealth	Clinic	Telehealth	
Perform physical examination (including height and weight)	X				Physical examinations to be completed before administration of study intervention.
Measure prevaccination temperature	X				If the temperature is >38°C (100.4°F), vaccination delay criteria apply. See Section 5.5.
Collect nonstudy vaccine information	X	X	X	X	
Collect prohibited medication use	X	X	X	X	
Confirm eligibility	X				
Review temporary delay criteria	X				
Collect blood sample for immunogenicity	~5 mL for children <10 years of age and ~10 mL for children 10 to <18 years of age		~5 mL for children <10 years of age and ~10 mL for children 10 to <18 years of age		Any AEs occurring up to 48 hours after the blood draw must be recorded (see Section 8.4.1).

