8.4.5.1. Exposure During Pregnancy

An EDP occurs if:

- A female participant is found to be pregnant while receiving or after discontinuing study intervention.
- A male participant who is receiving or has discontinued study intervention inseminates a female partner.
- A female nonparticipant is found to be pregnant while being exposed or having been exposed to study intervention because of environmental exposure. Below are examples of environmental EDP:
 - A female family member or healthcare provider reports that she is pregnant after having been exposed to the study intervention by inadvertent product administration via needlestick or skin contact.
 - A male family member or healthcare provider who has been exposed to the study intervention by inadvertent product administration via needlestick or skin contact then inseminates his female partner prior to or around the time of conception.

The investigator must report EDP to Pfizer Safety within 24 hours of the investigator's awareness, irrespective of whether an SAE has occurred. The initial information submitted should include the anticipated date of delivery (see below for information related to termination of pregnancy).

- If EDP occurs in a participant/participant's partner, the investigator must report this information to Pfizer Safety on the Vaccine SAE Reporting Form and an EDP Supplemental Form, regardless of whether an SAE has occurred. Details of the pregnancy will be collected after the start of study intervention and until the participant's last visit of the study.
- If EDP occurs in the setting of environmental exposure, the investigator must report information to Pfizer Safety using the Vaccine SAE Reporting Form and EDP Supplemental Form. Since the exposure information does not pertain to the participant enrolled in the study, the information is not recorded on a CRF; however, a copy of the completed Vaccine SAE Reporting Form is maintained in the investigator site file.

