Follow-up is conducted to obtain general information on the pregnancy and its outcome for all EDP reports with an unknown outcome. The investigator will follow the pregnancy until completion (or until pregnancy termination) and notify Pfizer Safety of the outcome as a follow-up to the initial EDP Supplemental Form. In the case of a live birth, the structural integrity of the neonate can be assessed at the time of birth. In the event of a termination, the reason(s) for termination should be specified and, if clinically possible, the structural

integrity of the terminated fetus should be assessed by gross visual inspection (unless preprocedure test findings are conclusive for a congenital anomaly and the findings are reported).

Abnormal pregnancy outcomes are considered SAEs. If the outcome of the pregnancy meets the criteria for an SAE (ie, ectopic pregnancy, spontaneous abortion, intrauterine fetal demise, neonatal death, or congenital anomaly), the investigator should follow the procedures for reporting SAEs. Additional information about pregnancy outcomes that are reported to Pfizer Safety as SAEs follows:

- Spontaneous abortion including miscarriage and missed abortion should be reported as an SAE;
- Neonatal deaths that occur within 1 month of birth should be reported, without regard to causality, as SAEs. In addition, infant deaths after 1 month should be reported as SAEs when the investigator assesses the infant death as related or possibly related to exposure to the study intervention.

Additional information regarding the EDP may be requested by the sponsor. Further follow-up of birth outcomes will be handled on a case-by-case basis (eg, follow-up on preterm infants to identify developmental delays). In the case of paternal exposure, the investigator will provide the participant with the Pregnant Partner Release of Information Form to deliver to his partner. The investigator must document in the source documents that the participant was given the Pregnant Partner Release of Information Form to provide to his partner.

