8.4.8. Adverse Events of Special Interest

- Diagnosis of Guillain-Barré syndrome
- Diagnosis of acute polyneuropathy without an underlying etiology
- Diagnosis of atrial fibrillation
- Preterm delivery (delivery at <37 0/7 weeks' gestation)
- Diagnosis of a hypertensive disorder of pregnancy

Details of the AESIs listed above are further defined in the investigator site file.

AESIs are examined as part of routine safety data review procedures throughout the clinical trial and as part of signal detection processes. Should an aggregate analysis indicate that these prespecified events occur more frequently than expected, eg, based on epidemiological data, literature, or other data, then this will be submitted and reported in accordance with Pfizer's safety reporting requirements. Aggregate analyses of safety data will be performed on a regular basis per internal SOPs.

All AESIs must be reported as an AE or SAE following the procedures described in Sections 8.4.1 through Section 8.4.4. An AESI is to be recorded as an AE or SAE on the CRF. In addition, an AESI that is also an SAE must be reported via PSSA or using the Vaccine SAE Reporting Form. The active collection period for AESIs is from the signing of the ICD until the end of the study for all participants.

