- Obtain details of any nonstudy vaccinations and prohibited concomitant medications and treatments as described in Section 6.9.
- Collect a blood sample (approximately 5 mL for children <10 years of age and approximately 10 mL for children 10 to <18 years of age) for immunogenicity.
- Collect a blood sample for PBMC isolation.
- Review ongoing reactogenicity e-diary symptoms reported as present on the last day of the e-diary and obtain stop dates. Record stop dates in the CRF if required.
- Record AEs, SAEs, AESIs, and NDCMCs as described in Section 8.4.
- Ask the participant's parent(s)/legal guardian to contact the site staff or investigator if a medically attended event (eg, doctor's visit, emergency room visit) or hospitalization occurs.
- Collect the participant's e-diary or assist the participant with removing the study application from his or her own personal device (if this has not been done already).
- Schedule an appointment for the participant for the next study visit.
- Complete the source documents.
- The investigator or an authorized designee completes the CRFs.

8.10.4. Visit 4 – 6-Month Follow-Up Visit (Telehealth; 175 to 189 Days After Visit 1)

- Contact the participant's parent(s)/legal guardian by telephone.
- Obtain details of any nonstudy vaccinations as detailed in Section 6.9.

- Record details of any of the prohibited medications specified in Section 6.9.1. Review ongoing reactogenicity e-diary symptoms reported as present on the last day of the e-diary and obtain stop dates. Record stop dates in the CRF if required.
- Record SAEs, AESIs, and NDCMCs as described in Section 8.4.
- Complete the source documents.
- The investigator or an authorized designee completes the CRFs.

8.11. Unscheduled Visit for Fever or a Grade 3 or Suspected Grade 4 Reaction

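### SAP 3.5.2 counts preterm delivery only up to study end but divides by all pregnant women, so a pregnancy still ongoing at the cut-off is counted as not preterm while its outcome is unknown

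*SAP*

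**What the plan says.** **Numerator.** SAP 3.5.2 lists two preterm events among the Tier 1 events: "preterm delivery (occurring from vaccination through the end of the study" and "preterm birth (occurring from vaccination through the end of the study".

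**Denominator.** The same section says the denominator for preterm delivery, preterm birth and "hypertensive disorders of pregnancy would be the number of pregnant women". It does not limit this to completed pregnancies or to pregnancies observed to a given gestation. SAP 6.6.1 attaches two-sided 95% confidence intervals to Tier 1 events.

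**Definition of the event.** Protocol 8.4.8 gives "Preterm delivery (delivery at <37 0/7 weeks" of gestation.

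**Length of observation.** The Schedule of Activities (Protocol 1.3) puts the last visit at "175 to 189 Days After Visit 1", and Protocol 4.1.2 gives about 6 months per participant. Protocol 4.4, however, defines the end of the study as the date on which the last participant makes the final visit.

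**Pregnancy follow-up.** Protocol 8.4.5.1 says two things. First: "Details of the pregnancy will be collected after the start of study intervention and until the participant's last visit of the study". Later: "The investigator will follow the pregnancy until completion (or until pregnancy termination", with the outcome then reported to the sponsor's safety group.

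**The concern.** Preterm delivery is a time-dependent classification. A continuing pregnancy cannot be called non-preterm until it passes 37 0/7 weeks. The SAP stops counting at study end and keeps every pregnancy in the denominator, so an unknown outcome is reported as a negative one. The proportion can then only be too low relative to the one obtained once all outcomes are known.

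The event has some importance to the programme. SAP 3.5.2 describes the Tier 1 list as requested by the FDA and clinically important. Protocol 2.3.1 reports preterm birth in the maternal study at 5.7% versus 4.7%, with a numerical imbalance in upper-middle-income countries, and notes that most of these events came more than 30 days after vaccination. Pregnancy in this trial is foreseeable, if unlikely: Protocol 5.2 does not exclude it, Appendix 3 on contraception is marked not applicable, and Protocol 5.3 provides for recording it.

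**Working it through.** **Inputs**
- Preterm threshold: 37 0/7 weeks = 37 × 7 = 259 days (Protocol 8.4.8).
- Last visit: 175 to 189 days after Visit 1 (Protocol 1.3).
- Assumption: 14 days from last menstrual period (LMP) to conception. The documents give no dating convention, so both are shown.
- Assumption: the SAP's pregnant women are pregnant participants.

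**1. The plan's own figure.** 175 / 30.44 = 5.75 months and 189 / 30.44 = 6.21 months. This agrees with the stated follow-up of about 6 months.

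**2. Greatest gestation at Visit 4 for a pregnancy that begins after vaccination**

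| Start of pregnancy | Formula | Day 175 | Day 189 | Days short of 259 |
|---|---|---|---|---|
| LMP on Day 1 | d / 7 | 25.0 weeks | 27.0 weeks | 84 to 70 |
| Conception on Day 1 | (d + 14) / 7 | 27.0 weeks | 29.0 weeks | 70 to 56 |

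Later starts give lower values. By Visit 4, only a pregnancy already at (259 − 189) / 7 = 10 weeks to (259 − 175) / 7 = 12 weeks at vaccination can have reached 37 weeks.

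**3. What the SAP rule does.** Let n be preterm deliveries inside the window, N all pregnancies, and k those still ongoing that later deliver preterm. The SAP reports n / N. The proportion with all outcomes known is (n + k) / N, which is never smaller.
- Two ongoing pregnancies are reported as 0/2 = 0%. The final value could be 0%, 50% or 100%. The exact upper 95% limit for 0/n is 1 − 0.025^(1/n), which is 84.2% for 0/2 and 97.5% for 0/1.
- One delivery at 28 weeks plus three ongoing is reported as 1/4 = 25%. The final value could be anywhere from 1/4 to 4/4.

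**4. A delivery inside the window is counted.** With conception on Day 1, a delivery at 28 weeks falls on day 196 − 14 = 182, which lies within the Visit 4 window. It is preterm and enters the numerator if that participant's visit is on or after that day.

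**5. Restricting the denominator to completed pregnancies is not a cure.** If the cut comes early, every birth so far from a pregnancy begun after vaccination is preterm. In the example with one delivery and three ongoing, the proportion becomes 1/1 = 100%. The denominator must be defined by the date on which 37 0/7 weeks is reached, whether or not delivery has occurred.

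**6. The other reading of the window.** Under Protocol 4.4 the cut-off is one calendar date for everyone. Early enrollees then have more than 189 days, by an amount that depends on the enrolment period, which is not given. Observation time varies with enrolment date. The dose groups are enrolled in sequence (Protocol 4.1.2), so it could also differ between groups in a table presented by vaccine group.

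**The case against.** Four arguments run the other way.

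- **The cut-off is not necessarily Visit 4.** Protocol 4.4 defines study end by the last participant, and the SAP names the 6-month follow-up visit when it means the individual's visit (SAP 6.5.2). This stands. A reader might infer that the preterm count certainly closes at day 175 to 189; the documents do not settle that. The first pregnancy sentence in Protocol 8.4.5.1, which ends at the participant's last visit, is consistent with the Visit 4 reading. Neither reading supplies a rule for pregnancies ongoing at the cut-off.
- **Not every post-vaccination pregnancy becomes a non-event.** A reader might infer that each one is classed as not preterm. That is too strong: step 4 shows that a delivery inside the window counts as preterm. Only ongoing pregnancies are affected, and this follows from the denominator sentence, not from an explicit instruction.
- **The outcomes will be known anyway.** Follow-up to completion in Protocol 8.4.5.1 should bring later outcomes to the sponsor's safety group. This stands only in part. The same section also limits collection of pregnancy details to the last visit, and the SAP does not say that later outcomes enter the Tier 1 table.
- **The numbers will be tiny.** The trial enrols about 60 to 120 children aged 2 to <18 years, is descriptive, and tests no hypothesis. Pregnancies are reported individually and adverse events of special interest are summarised separately (SAP 6.1.2.2). With 0 to 2 pregnancies (an assumption), the interval is so wide that the point estimate would hardly mislead. This stands in full and limits the weight of the point.

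**Conclusion.** The numerator window and the denominator in SAP 3.5.2 do not match. A pregnancy still ongoing at the cut-off is reported as not preterm although its outcome is unknown, which biases the proportion downward. On the Visit 4 reading, a pregnancy begun after vaccination is at least 8 weeks (56 days) short of 37 weeks at the last visit. It can be recorded as preterm if delivered by then, but while it continues it cannot be confirmed as non-preterm. On the study-level reading the shortfall is smaller for early enrollees by an unknown amount, and the window varies with enrolment date.

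The gestation figures rest on the stated visit window and the 14-day LMP-to-conception assumption. Pregnancies ending in loss or termination are set aside, because SAP 3.5.2 does not address them. The documents give no distribution of conception dates, so they do not support any estimate of the share of pregnancies affected.

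This is a minor correction. It affects one descriptive rare-event table and none of the main reactogenicity, adverse event or immunogenicity results.

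**What to change.** In SAP 3.5.2:

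1. Count preterm delivery and preterm birth through pregnancy outcome, taking outcomes after the last visit from the follow-up to completion in Protocol 8.4.5.1.
2. Restrict the denominator to pregnancies whose 37 0/7-week date falls on or before the data cut, whether or not they have delivered.
3. List every other pregnancy individually with its status: preterm delivery already observed, or outcome not yet known.
4. If any pregnancy is unresolved at the final analysis, give the listing in place of the rate and report the outcome in an addendum.
5. Say whether study end, wherever it remains as a cut-off in this section, means the participant's last visit or the Protocol 4.4 date.

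In Protocol 8.4.5.1, reconcile the sentence that stops collection of pregnancy details at the last visit with the one that follows the pregnancy to completion.

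The cost is a few sentences of SAP text, a protocol clarification, and one merge with outcomes held in safety reporting. The drawback is that a rate may not be available at the final analysis and an addendum may be needed. With so few pregnancies expected, a listing loses little.

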## 4. ANALYSIS SETS (POPULATIONS FOR ANALYSIS)

Data for all participants will be assessed to determine if participants meet the criteria for inclusion in each analysis population prior to unblinding and releasing the database and classifications will be documented per standard operating procedures.

For purposes of analysis, the following analysis sets are defined:

Participant Analysis Set	Description	Applicable Analysis
Enrolled population	All participants who have a signed ICD.	Study conduct such as participant disposition
Randomized population	All enrolled participants who are assigned a randomization number in the IRT system.	Immunogenicity analysis population disposition
E-diary safety population	All participants who receive the study intervention have at least 1 day of e-diary data transferred.	Primary safety endpoint analysis
Safety population	All enrolled participants who receive the study intervention.	Primary safety endpoint analysis

Defined Analysis Set	Description	Applicable Analysis
Evaluable immunogenicity population	This population will be defined for all participants who meet the following criteria:	Primary analysis population for immunogenicity endpoints (secondary)
	Are eligible for the study;	
	Receive the intervention;	
	Have the 1-month postvaccination blood collection 27 through 42 days after vaccination;	
	Have at least 1 valid and determinate assay result 1 month after vaccination;	
	Have no major protocol violations from vaccination through the 1-month postvaccination blood draw.	
mITT immunogenicity population	All participants who are randomized and have at least 1 valid and determinate assay result at any time point after receiving the study intervention.	Supplemental analysis on secondary immunogenicity endpoints

#### 5. GENERAL METHODOLOGY AND CONVENTIONS

## 5.1. Hypotheses and Decision Rules

There is no statistical hypothesis.

#### **5.2. General Methods**

Unless otherwise stated, "CI" refers to a 2-sided CI in this document for 95% CI.

Descriptive statistics for binary variables are the proportion (%) and the numerator (n) and the denominator (N) used in the proportion calculation. The 95% CI for percentage, and for the difference in percentages, may also be presented, where appropriate.

Unless otherwise specified, descriptive statistics for continuous variables are n, mean, median, standard deviation, minimum, and maximum.

The subsections below describe the analysis for different types of endpoints.

## 5.2.1. Analyses for Binary Data

Descriptive statistics for binary variables are the proportion (%) and the numerator (n) and the denominator (N) used in the proportion calculation. The 95% CI for percentage, and for the difference in percentages, will also be presented, where applicable.

1. The 95% CI for the proportion (within–vaccine group) will be constructed by the Clopper-Pearson method described by Newcombe. The 95% CI will be presented in terms of percentage.

